10.1. Appendix 1: Time & Events

10.1.1. Protocol Defined Time & Events

Time and Events Table: Parts 1a, 1b, 2a, 2b, and 3

Procedure	Screening (up to 30 days prior to Day 1)		Part 1a - Relative Bioavailability: Periods 1, 2, and 3 Part 1b - Food Effect: Periods 1 and 2 Part 2 - Pharmacokinetics: Periods 1 and 2 Part 3 - Pharmacokinetics – Fed State: Periods 1, 2, and 3													Follow- up (5 to 7 days post-last dose)	
			Day -1 ^a	Pre-dose	0h	0.5h	1h	1.5h	2h	2.5h	3h	4h	6h	8h	12h	24h	
Admission to Unit		X															
Informed Consent	X																
Demographics including BMI	X																
Full physical examination including height and weight ^b	X																
Brief physical examination ^b		X															X
Medical/medication/drug/alcohol history	X																
12-lead ECG ^c	X	X	X						X					X	X	X	
Vital signs ^d	X	X	X						X					X	X	X	
Drug/alcohol/cotinine screen	X	X															
Serum pregnancy, FSH, and estradiol (women)	X	X															X
HIV antibody, HBsAg, and hepatitis C antibody screen	X																
Safety laboratory tests ^e	X	X															X
Study drug administration ^f				X													
Pharmacokinetic sampling				X	X	X	X	X	X	X	X	X	X	X	X	X	
Urine collection for pharmacokinetics (Parts 1a, 2, and 3 only) ^g				X						X	X	X	X	X	X	X	

Time and Events Table: Parts 1a, 1b, 2a, and 2b, cont.

Procedure	Screening (up to 30 days prior to Day 1)	Day -1 ^a	Part 1a - Relative Bioavailability: Periods 1, 2, and 3													Follow-up (5 to 7 days post- last dose)		
			Part 1b - Food Effect: Periods 1 and 2															
			Part 2 - Pharmacokinetics: Periods 1 and 2															
Pre-dose	0h	0.5h	1h	1.5h	2h	2.5h	3h	4h	6h	8h	12h	24h	36h	Day 3	48h			
Pharmacogenetic sample ^h				←=====→														
AE/SAE Review	X			←=====→												X		
Concomitant medication review		X		←=====→												X		
Discharge ⁱ															X			
Outpatient visit	X															X		

AE = adverse event, BMI = body mass index, ECG = electrocardiogram, FSH = follicle-stimulating hormone, HBsAg = hepatitis B surface antigen, HIV = human immunodeficiency virus, SAE = serious adverse event

^a The Day -1 visit occurs in Period 1 only. Periods 2 (all parts) and 3 (Parts 1a and 3 only) begin on Day 1.

^b A complete physical examination will include at a minimum, assessment of the cardiovascular, respiratory, GI, and neurological systems. Height and weight will also be measured and recorded. A brief physical examination will include, at a minimum, assessments of the skin, lungs, cardiovascular system, and abdomen (liver and spleen)

^c Triplicate 12-lead ECGs will be measured in semi-supine position after 5 minutes rest and obtained at least 5 minutes apart on Day -1. Single 12-lead ECGs will be measured in semi-supine position after 5 minutes rest at all other time points during the study.

^d Single vital signs will be measured in semi-supine position after 5 minutes rest and will include systolic and diastolic blood pressure, and heart rate. Body temperature and respiratory rate will be collected at Screening only.

^e Safety laboratory tests include serum chemistry, hematology, and urinalysis.

^f Subjects will fast from food and drink (except water) for at least 10 hours before study drug administration on Day 1 of each period. For the fed group of the food effect evaluation in Part 1b, study drug will be administered within 30 minutes after the completion of a moderate fat meal. For Part 3, study drug will be administered within 30 minutes after completion of a standard Japanese meal.

^g Urine collection intervals (Parts 1a, 2 and 3 only) for subjects include 0 (pre-dose), 0 to 2 hours, 2 to 4 hours, 4 to 6 hours, 6 to 8 hours, 8 to 12 hours, 12 to 24 hours, 24 to 36 hours, and 36 to 48 hours.

^h For subjects who consent only: collect 1 pharmacogenetic sample after the start of dosing (preferably Day 1). Informed consent for optional pharmacogenetic research must be obtained before collecting a sample.

ⁱ For Parts 1a and 3, subjects will be discharged from the clinic research unit on Day 3 of Period 3. For Parts 1b and 2, subjects will be discharged on Day 3 of Period 2.

10.2. Appendix 2: Treatment States and Phases

10.2.1. Treatment States

Assessments and events will be classified according to time of occurrence relative to the start and/or stop date of the study treatment for the respective treatment period.

10.2.1.1. Treatment States for Safety Data

Treatment State	Definition
Pre-Treatment	Date/Time < Study Treatment Start Date/Time
On-Treatment	Study Treatment Start Date/Time ≤ Date/Time ≤ Study Treatment Stop Date/Time + 2 Days
Post-Treatment	Date/Time > Study Treatment Stop Date/Time +2 Days

NOTES:

- If the study treatment stop date is missing then the assessment will be considered to be On-Treatment

10.2.1.2. Treatment States for AE Data

Treatment State	Definition
Pre-Treatment	AE Start Date/Time < Study Treatment Start Date/Time
On-Treatment	If AE onset date/time is on or after treatment start date/time & on or before the treatment stop date/time with 2 days lag time Study Treatment Start Date/Time ≤ AE Start Date/Time ≤ Study Treatment Stop Date/Time + 2 Days
Post-Treatment	If AE onset date/time is after the treatment stop date/time with 2 days lag time AE Start Date/Time > Study Treatment Stop Date/Time + 2 days
Onset Time	If Treatment Start Date/Time > AE Onset Date/Time = AE Onset Date - Treatment Start Date
Since First Dose (Days)	If Treatment Start Date/Time ≤ AE Onset Date/Time = AE Onset Date - Treatment Start Date +1 Missing otherwise
Duration (Days)	AE Resolution Date – AE Onset Date + 1
Drug-related	If relationship is marked 'YES' on eCRF OR value is missing

NOTES:

- If the study treatment stop date is missing then the AE will be considered to be On-Treatment.

10.3. Appendix 3: Data Display Standards & Handling Conventions

10.3.1. Study Treatment & Sub-group Display Descriptors

Treatment Group Descriptions				
Study Part	Treatment Group		Data Displays for Reporting	
	Code	Description	Description	Order [1]
1a	A	Gepotidacin 1500 mg (3 × 500 mg) reference capsules	Reference	1
1a, 2 ^[3]	B	Gepotidacin 1500 mg (2 × 750 mg) RC tablets	RC 1500 mg	2
1a, 2 ^[3]	C	Gepotidacin 1500 mg (2 × 750 mg) HSWG tablets	HSWG 1500 mg	3
1b	D	Gepotidacin 1500 mg (2 × 750 mg) RC or HSWG tablets selected from Part 1a – fasted	RC 1500 mg Fasted or HSWG 1500 mg Fasted ^[2]	4
1b, 3	E	Gepotidacin 1500 mg (2 × 750 mg) RC or HSWG tablets selected from Part 1a – fed	RC 1500 mg Fed or HSWG 1500 mg Fed ^[2]	5
2	F	Gepotidacin 3000 mg (4 × 750 mg) RC or HSWG tablets selected from Part 1a	RC 3000 mg or HSWG 3000 mg ^[2]	6
3	G	Gepotidacin 2250 mg (3 × 750 mg) RC or HSWG tablets selected from Part 1a – fed	RC 2250 mg Fed or HSWG 2250 mg Fed ^[2]	7
3	H	Gepotidacin 3000 mg (4 × 750 mg) RC or HSWG tablets selected from Part 1a – fed	RC 3000 mg Fed or HSWG 3000 mg Fed ^[2]	8
3	I	Placebo	Placebo	9

NOTES:

1. Order represents treatments being presented in TFL, as appropriate.
2. The use of "RC" vs "HSWG" will be determined after study part 1a.
3. In part 2, one of Treatment B or Treatment C (determined after study part 1a) will be administered in period 1.

10.3.2. Baseline Definition & Derivations

10.3.2.1. Baseline Definitions

For all endpoints (expect as noted in the table) the baseline value will be the latest pre-dose assessment and are applicable to each period.

Table 9 Baseline Definitions

Parameter	Study Assessments Considered As Baseline			Baseline Used in Data Display
	Screening	Day -1	Day 1 (Pre-Dose)	
Safety				
Hematology	X	X		Day -1
Clinical Chemistry	X	X		Day -1
12 Lead ECG	X	X	X	Day 1 (Pre-dose)
Vital Signs	X	X	X	Day 1 (Pre-dose)

NOTES :

- Unless otherwise stated, the mean of replicate assessments at any given time point will be used as the value for that time point.

10.3.2.2. Derivations and Handling of Missing Baseline Data

Definition	Reporting Details
Change from Baseline	= Post-Dose Visit Value – Baseline

NOTES :

- Unless otherwise specified, the baseline definitions specified in Section 10.3.2.1 Baseline Definitions will be used for derivations for endpoints / parameters and indicated on summaries and listings.
- Unless otherwise stated, if baseline data is missing no derivation will be performed and will be set to missing.
- The baseline definition will be footnoted on all change from baseline displays.

10.3.3. Reporting Process & Standards

Reporting Process
Software

 The currently supported versions of SAS and WinNonlin software will be used.
Analysis Datasets

 Analysis datasets will be created according to CDISC standards (SDTM IG Version 3.1.3 & ADaM IG Version 1.0]. For creation of ADaM datasets (ADCM/ADAE), the same version of dictionary datasets will be implemented for conversion from SI to SDTM.
Generation of RTF Files

 RTF files will be generated for all reporting efforts described in the RAP.

Reporting Standards
General

 The current GSK Integrated Data Standards Library (IDSL) will be applied for reporting, unless otherwise stated: 
 4.03 to 4.23: General Principles 5.01 to 5.08: Principles Related to Data Listings 6.01 to 6.11: Principles Related to Summary Tables

Reporting Standards	

 ○ 7.01 to 7.13: Principles Related to Graphics 	
Formats	

 ● All data will be reported according to the actual treatment the subject received unless otherwise stated. ● GSK IDSL Statistical Principles (5.03 & 6.06.3) for decimal places (DP's) will be adopted for reporting of data based on the raw data collected. ● Numeric data will be reported at the precision collected on the eCRF. ● The reported precision from non eCRF sources will follow the IDSL statistical principles but may be adjusted to a clinically interpretable number of DP's. 	
Planned and Actual Time	

 ● Reporting for tables, figures and formal statistical analyses : 
 ○ Planned time relative to dosing will be used in figures, summaries, statistical analyses and calculation of any derived parameters, unless otherwise stated. ○ The impact of any major deviation from the planned assessment times and/or scheduled visit days on the analyses and interpretation of the results will be assessed as appropriate. ● Reporting for Data Listings: 
 ○ Planned and actual time relative to study drug dosing will be shown in listings (Refer to IDSL Statistical Principle 5.05.1). ○ Unscheduled or unplanned readings will be presented within the subject's listings. ○ Visits outside the protocol defined time-windows (i.e. recorded as protocol deviations) will be included in listings but omitted from figures, summaries and statistical analyses. 	
Unscheduled Visits	

 ● Unscheduled visits will not be included in summary tables. ● Unscheduled visits will not be included in figures. ● All unscheduled visits will be included in listings. 	
Descriptive Summary Statistics	
Continuous Data	Refer to IDSL Statistical Principle 6.06.1
Categorical Data	N, n, frequency, %
Reporting of Pharmacokinetic Concentration Data	
Descriptive Summary Statistics	
Refer to IDSL Statistical Principle 6.06.1
 
 ● NQs at the beginning of a subject profile (i.e. before the first incidence of a measurable concentration) are deemed to be zero as it is assumed that in this circumstance no drug is yet measurable in the blood. ● For NQs at the end of the subject profile (i.e. after the last incidence of a measurable concentration); 
 ● for individual plots and pharmacokinetic analyses these are dropped (set to missing) as they do not provide any useful

Reporting Standards	
	
information (and can erroneously indicate that absolutely no drug is present)
 
 for summary statistics these are set to 0 (to avoid skewing of the summary statistics) Individual NQs which fall between two measurable concentrations are set to missing (individual values of this nature are assumed to be an anomaly) If two or more NQ values occur in succession between measurable concentrations, the profile will be deemed to have terminated at the last measurable concentration prior to these NQs. For the purpose of individual subject plots, these NQs will be set to 0, and the subsequent measurable concentrations will be retained. For the derivation of pharmacokinetic parameters, these NQs and any subsequent measurable concentrations will be omitted (set to missing).
Reporting of Pharmacokinetic Parameters	
Descriptive Summary Statistics. (Log Transformed)	
N, n, geometric mean, 95% CI of geometric mean, standard deviation (SD) of logged data and between subject coefficient of variation (CV_b (%)) will be reported.
 $CV_b (\%) = \sqrt{(\exp(SD^2) - 1) * 100}$ 
[NOTE: SD = SD of log transformed data]

Parameters Not Being Log Transformed	T _{max} , first point, last point and number of points used in the determination of λ _z .
Parameters Not Being Summarised	Additionally include t _{max} , first point, last point and number of points used in the determination of λ _z .
Listings	Include the first point, last point and number of points used in the determination of λ _z .
Graphical Displays	

 Refer to IDSL Statistical Principals 7.01 to 7.13. 	

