On Day 1 (Period 1), subjects will receive a single 1500-mg (2×750 mg) dose of gepotidacin tablet (RC or HSWG) selected from Part 1a. On Day 1 of Period 2, subjects will receive a single 3000-mg (4×750 mg) dose of gepotidacin tablet (RC or HSWG) selected from Part 1a. There will be a washout period of at least 3 days between doses.

Subjects will remain in the clinical research unit from Day -1 until Day 3 of Period 2 after all scheduled PK and safety assessments have been completed, and will return to the clinic for a Follow-up visit approximately 5 to 7 days after the final dose of study drug. The duration of the study (from Screening to the Follow-up visit) will be approximately 41 days.

Part 3: Pharmacokinetics in Japanese Subjects - Fed State

- Treatment E: Gepotidacin 1500 mg (2 × 750 mg) RC or HSWG tablets - fed
- Treatment G: Gepotidacin 2250 mg (3 × 750 mg) RC or HSWG tablets - fed
- Treatment H: Gepotidacin 3000 mg (4 × 750 mg) RC or HSWG tablets - fed
- Treatment I: Placebo tablets - fed

On Day 1 (Period 1), subjects will be stratified by gender in a 1:1 ratio and randomly assigned (10 active: 2 placebo) to receive gepotidacin tablet (RC or HSWG) selected from Part 1a in an ascending manner (Treatments E, G, and H) on Day 1 of Periods 1, 2, and 3, respectively, or placebo. For each period, a sentinel group of up to 4 subjects will be dosed with study drug and evaluated for safety and tolerability prior to dosing the remaining subjects. There will be a washout period of at least 3 days between doses. The adverse event profiles will be reviewed before escalating to the next dose. Subjects will remain in the clinical research unit from Day -1 until Day 3 of Period 3 after all scheduled PK and safety assessments have been completed, and will return to the clinic for a Follow-up visit approximately 5 to 7 days after the final dose of study drug. The duration of the study (from Screening to the Follow-up visit) will be approximately 44 days.

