4.4. Design Justification

The study design for Part 1a is commonly used when evaluating relative bioavailability of a drug entity in subjects. It is based on recommendations given in the US Food and Drug Administration (FDA) draft guidance for industry, Bioavailability and Bioequivalence Studies Submitted in NDAs or INDs — General Considerations [DHHS, 2014].

The study design for Part 1b is commonly used when evaluating the effect of food on a drug entity in subjects. It is based on recommendations given in the US FDA draft guidance for industry, Food-Effect Bioavailability and Fed Bioequivalence Studies [DHHS, 2002].

The study design for Part 2 is commonly used when evaluating pharmacokinetics of a drug entity in subjects from different ethnic groups. The fixed-sequence design allows for dosing of a lower dose followed by a higher dose within a subject and requires fewer subjects for PK evaluation compared with a parallel cohort. Pharmacokinetic data obtained from this group would satisfy regulatory guidelines and provide dosing recommendations for future Phase III studies in Japanese subjects.

The study design for Part 3 is commonly used when evaluating pharmacokinetics of a drug entity in subjects from different ethnic groups. The fixed-sequence design allows for dosing of a lower dose followed by escalating doses within a subject and requires fewer subjects for PK evaluation compared with a parallel cohort. The fed state will evaluate whether food improves tolerability at higher doses of gepotidacin. Pharmacokinetic data obtained from this group would satisfy regulatory guidelines and provide dosing recommendations under fed conditions for future Phase III studies in Japanese subjects.

Gepotidacin exhibits linear and time-independent pharmacokinetics, which indicates a single-dose study is adequate to achieve study objectives. A multiple-dose study is not necessary since there are no safety concerns with metabolites of this study drug.

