5.4.3. Gastrointestinal Stopping Criteria

Subjects experiencing Grade 3 or Grade 4 AEs (confluent pseudomembranes or ulcerations OR mucosal bleeding with minor trauma; tissue necrosis OR diffuse spontaneous mucosal bleeding OR life-threatening consequences, e.g., aspiration, choking) will be followed as appropriate until resolution of the AE(s).

Furthermore, subjects who experience diarrhea or enteritis should be evaluated with additional fecal occult blood tests and stool cultures as deemed appropriate by the investigator as outlined in [Appendix 8](#) and [Appendix 9](#).

For Part 3, subjects who experience diarrhea should also be evaluated using the guidelines detailed in [Table 8](#)

Table 8 Part 3 Management of Gastrointestinal Symptoms - Diarrhea

Diarrhea	Treatment Strategy
Grade 1	Initiate supportive care including loperamide.
Grade 2	Initiate supportive care including loperamide. Consider discontinuation of subject from the study upon discussion with medical monitor.
Grades 3 or 4	Above plus consider IV hydration, hospital admission and prophylactic antibiotics as appropriate. Withhold study drug(s) until diarrhea has resolved to ≤Grade 1, continue diarrheal prophylaxis. Discontinue subject from the study upon discussion with medical monitor.

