9.2. Sample Size Considerations

9.2.1. Sample Size Assumptions

Sample size is largely based on feasibility; however, some justification is provided below.

Part 1a – Relative Bioavailability:

The sample size of 24 PK parameter population subjects will be used based on feasibility to address the objectives of Part 1a of the study.

There are no estimates for the coefficient of variation (CV) of HSWG for any PK parameters. An assumed CV of 27.5% for a PK parameter implies that the sample size of 24 PK parameter evaluable subjects will provide at least 80% power to demonstrate equivalence of the PK parameter. Equivalence is demonstrated when 90% confidence interval (CI) for the ratio of Test:Reference of the PK parameter will be within 0.8 to 1.25 following log transformation.

Two different test formulations are being used in this study. No adjustment for pre-planned multiple comparisons are made.

The total sample size of 27 subjects (9 subjects in 3 sequences) will be randomized to ensure 24 PK parameter evaluable subjects with PK parameter estimates from the reference and at least one test formulation.

Part 1b – Food Effect:

A sample size of 16 subjects will be randomized (8 per sequence) based on feasibility to address the objectives of Part 1b of the study.

This sample size will ensure equivalence (as specified in sample size assumption in Part 1a) with 80% power with an assumed CV of 22%.

Part 2 – Pharmacokinetics:

A sample size of approximately 10 subjects will be used in Part 2 based on feasibility to address the objectives of Part 2 of the study.

Part 3 – Pharmacokinetics - Fed State:

A sample size of 12 subjects (ideally 6 male, 6 female) will be randomized (10 active: 2 placebo) based on feasibility to address the objectives of Part 3 of the study.

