9.4.2. Secondary Analyses

Safety Analyses

The following safety evaluations will be performed:

- Monitoring for AEs
- Changes in routine clinical laboratory parameters including serum chemistry, hematology, and urinalysis
- Clinically significant changes in vital sign measurements or physical examination findings
- Changes in 12-lead ECG measurements

Safety endpoints will include AEs, clinical laboratory results (serum chemistry [including liver function parameters], hematology, and urinalysis), vital sign measurements (systolic and diastolic blood pressure and heart rate), 12-lead ECG measurements, and physical examination findings.

All safety data will be presented in the data listings. Subject demographics, medical history, and prior and concomitant medications will be summarized by group using descriptive statistics. For continuous variables, these summaries will include sample size, mean, median, SD, minimum, and maximum.

For categorical variables, the summaries will include frequencies and corresponding percentages. No inferential hypothesis testing will be performed on the safety variables.

Adverse events will be coded using the MedDRA classification system.

Treatment-emergent AEs will be defined as any AEs, regardless of relationship to investigational product, that occur after the dose of investigational product. All AEs will be summarized by group at AE onset for the overall number of AEs and the percentage of subjects who experience them. The total number of AEs will be summarized by group and overall. Listings for the subsets of SAEs and treatment-related SAEs will be provided. The number of SAEs will be summarized. The incidence of AEs will also be summarized by system organ class and preferred term.

Clinical laboratory results, vital sign measurements (systolic and diastolic blood pressure and heart rate), and 12-lead ECG results will be summarized by change from baseline. Clinical laboratory values that are outside of the reference ranges will be flagged and evaluated for clinical significance by the investigator. Any ECG abnormalities, including but not limited to a QTc >500 msec or increase in QTc from the baseline ECG of ≥ 60 msec, will be summarized by group.

Detailed descriptions of the analyses in this study will be presented in the RAP.

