4. ANALYSIS POPULATIONS

Population	Definition / Criteria	Endpoint(s) Evaluated
Safety Population	
 Will consist of all subjects who receive at least 1 dose of study drug and have at least 1 post dose safety assessment. This population will be based on the treatment which the subject actually received. 	
 Study Population Safety
PK Population	
 Will consist of all subjects who received at least 1 dose of gepotidacin and have evaluable PK data for gepotidacin. 	
 PK Concentration
PK Parameter Population	
 Will consist of all subjects in the PK Population, for whom valid and evaluable PK parameters were derived. This population will be used in the assessment and characterization of PK parameters. 	
 PK Parameters

NOTES:

- Please refer to [Appendix 11](#) which details the population to be used for each display being generated.

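### AE percentages at 3000 mg fed may be understated, and may compare too well with 3000 mg fasted, if subjects are discontinued for GI events at 1500 or 2250 mg

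*SAP*

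**What the plan says.** In Part 3, protocol 4.2 has active subjects receive gepotidacin "in an ascending manner (Treatments E, G, and H) on Day 1 of Periods 1, 2, and 3, respectively, or placebo", that is, 1500, 2250 and 3000 mg fed in the same people. Protocol 9.2.1 gives the size: "A sample size of 12 subjects (ideally 6 male, 6 female) will be randomized (10 active: 2 placebo) based on feasibility". It states no AE rate.

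Protocol Table 8 (section 5.4.3, Part 3 only) grades the response to diarrhea. Grade 1 gets supportive care. Grade 2 adds "Consider discontinuation of subject from the study upon discussion with medical monitor". Grades 3 and 4 direct discontinuation after that discussion.

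Part 2 is also a fixed ascending sequence, 1500 then 3000 mg fasted, in about 10 subjects. The GI row of the risk table in protocol 4.6.1 provides for permanent discontinuation at Grade 3 or 4 and is not confined to Part 3.

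On reporting, SAP 10.3.3 has the sentence "All data will be reported according to the actual treatment the subject received unless otherwise stated". SAP section 4 says of the Safety Population: "This population will be based on the treatment which the subject actually received". Protocol 9.4.2 adds: "All AEs will be summarized by group at AE onset for the overall number of AEs and the percentage of subjects who experience them". Neither document writes out the denominator of that percentage.

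On purpose, protocol 4.4 says: "The fed state will evaluate whether food improves tolerability at higher doses of gepotidacin". Protocol Appendix 11 records that Part 3 was added because of tolerability at 3000 mg fasted in Part 2.

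**The concern.** Read together, these rules make the 3000 mg fed column a column of those who got that far. A subject discontinued for diarrhea at 1500 or 2250 mg counts in the column for the dose received (SAP 10.5.1 keeps those data) but drops out of numerator and denominator at 3000 mg. If people who react at a lower dose are also more likely to react at a higher one, the remaining group is less susceptible than the group that started.

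Part 2 is filtered in the same way, but over one earlier dose and without the Table 8 option at Grade 2. The difference in filtering, not filtering as such, could favour the fed column. What is at stake is the answer to the stated question of whether food helps at higher doses: part of an apparent benefit could come from who was left to dose. SAP Tables 2.1 to 2.4 contain no row for subjects lost during escalation.

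**Working it through.** The plan gives no AE or withdrawal rate, so there is no figure of its own to reproduce. The one consistency check is allocation: 12 × 5/6 = 10 active, so 5:1 in the SAP agrees with 10:2 in the protocol. All rates, correlations and severity cut-offs below are assumptions.

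**1. Chance that anyone is removed before 3000 mg.** With removal risk p per dose and 10 active subjects, this is 1 − (1 − p)^20 in Part 3 (two earlier doses) and 1 − (1 − p)^10 in Part 2 (one).
- p = 1%: 18% and 10%
- p = 5%: 64% and 40%
- p = 10%: 88% and 65%

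**2. Effect in counts.** Suppose 4 of 10 would have the event at 3000 mg and k of those four are removed earlier. The column shows (4 − k)/(10 − k): 4/10 = 40% for k = 0, 3/9 = 33% for k = 1, 2/8 = 25% for k = 2, 1/7 = 14% for k = 3. The exact 95% interval for 2/8 is 3% to 65%.

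**3. Upper-end case.** Assume Grade 2 or worse diarrhea in 10%, 20% and 40% at 1500, 2250 and 3000 mg, no food effect, and that anyone affected at one dose is affected at every higher dose.
- All affected removed: Part 3 shows (0.40 − 0.20)/(1 − 0.20) = 25%; Part 2 shows (0.40 − 0.10)/(1 − 0.10) = 33%.
- Half removed after each affected dose: Part 3 shows (0.025 + 0.05 + 0.20)/0.875 = 31%; Part 2 shows (0.05 + 0.30)/0.95 = 37%.
- With 10%, 30% and 50% and all removed: 0.20/0.70 = 29% and 0.40/0.90 = 44%.

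Part 2 would show the full 40% (or 50%) if nobody were discontinued there.

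**4. Less extreme carry-over.** A latent-severity (probit) simulation of 400,000 subjects used any-grade event rates of 10/20/40% and 20/40/60% at the three doses. Grade 2 and Grade 3 began 0.5 and 1.2 SD above the event threshold. True rates fed and fasted were equal, and the same removal rule applied in both parts. At correlation 0 neither column was biased. At correlations 0.5 to 0.8:

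| Removed | True rate at 3000 mg | Part 3 column | Part 2 column |
|---|---|---|---|
| Grade 3/4 only | 40% | 38.5–38.8% | 39.5–39.7% |
| Grade 3/4 only | 60% | 56.7–57.0% | 59.2–59.3% |
| Grade 3/4 and all Grade 2 | 40% | 33.8–35.5% | 37.8–38.5% |
| Grade 3/4 and all Grade 2 | 60% | 48.2–51.0% | 56.1–56.9% |

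The Part 3 understatement is about 1 to 3 points in the first two rows and 5 to 12 in the last two. The fed–fasted gap is about 1 to 2.5 and 3 to 8 points. If all Grade 2 cases left in Part 3 but only Grade 3/4 cases left in Part 2, the gap at matching correlations would run from 39.7 − 35.5 = 4.2 to 59.2 − 48.2 = 11.0 points.

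**The case against.** A reader might infer that Table 8 takes subjects with diarrhea out of the study, so that 3000 mg fed is bound to look better tolerated than it is and better than 3000 mg fasted. The documents do not support that. Grade 1 diarrhea leads to no removal, Grade 2 removal is discretionary, and only Grades 3 and 4 carry a direction to discontinue. Part 2 has its own earlier dose and the Grade 3/4 rule in protocol 4.6.1, and protocol 5.4 lets the investigator withdraw any subject for safety. No withdrawal rate is given anywhere.

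The sentence in SAP 10.3.3 is an ordinary as-treated rule. That the 3000 mg denominator is the subjects dosed with Treatment H is the natural reading, not stated text.

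Much of the information will also be visible. A disposition table (1.2) and listings of withdrawals, all AEs, and AEs leading to withdrawal (2, 14 and 17) are planned, and categorical summaries show N. With 10 active subjects one person is 10 points, intervals are wide, safety analysis is descriptive, and the SAP lists no fed-versus-fasted AE display.

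All of this limits the size and certainty of the point. It does not remove it: protocol 4.4 invites the comparison, and none of those displays connects an earlier withdrawal to incidence at the next dose.

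**Conclusion.** The point holds conditionally. The 3000 mg fed percentages may be understated, and may compare too well with Part 2, if subjects are discontinued for GI events at 1500 or 2250 mg and AEs are correlated within subject. If either condition fails there is no bias. With correlations of 0.5 to 0.8 the understatement is about 1 to 3 points with Grade 3/4 removal only and 5 to 12 points if every Grade 2 case also leaves. The 15-point case (25% shown for a true 40%) needs perfect carry-over and removal of everyone affected, and should be read as an upper end. This merits an inexpensive addition to the reporting, not a change of design or of the as-treated tables.

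**What to change.** Keep the as-dosed percentages. Beside them, in SAP Table 2.1 or a small companion table for Parts 2 and 3, show for each dose:
- the number dosed;
- the number not reaching that dose, with the reason;
- a supplementary row: subjects with diarrhea at this dose, or withdrawn for a GI AE at a lower dose, divided by all originally enrolled subjects who started Period 1 on active drug; and the same for any GI AE.

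Table 2.3 is not a suitable place, because it covers only common non-serious events. Only GI withdrawals should count in the numerator, so that a withdrawal for QTc, ALT or rash is not read as diarrhea. Show replacement subjects separately and state at which dose they enter, since protocol 4.3 does not say.

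Report both figures as a bracket in any statement about higher doses or fed versus fasted. The row assumes that intolerance carries upward. With two of 10 removed and AEs in fact independent at 40%, it would read (2 + 0.4 × 8)/10 = 52%. It also counts subjects lost for other reasons as event-free, which is why the number not reaching each dose must stand beside it. It does not remove the other differences between two non-randomized cohorts: Part 2 is open-label, Part 3 is blinded, and Table 8 provides for loperamide in Part 3 only.

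Separately, the sponsor should reconcile the discontinuation wording. Protocol 4.6.1 speaks of permanent discontinuation at Grade 3 or 4, while the Grade 3/4 row of Table 8 speaks both of withholding until resolution and of discontinuing.

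The cost is one derived display from disposition and AE data already collected.
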